#### **8.4.5. Adverse Events of Special Interest**

Meningococcal infections will be collected as AESIs.

## 8.5. Treatment of Overdose

For this study, any dose of study drug greater than that specified in the protocol will be considered an overdose. If dose cannot be established during the Randomized Controlled Period due to blinding, suspected overdose should be defined by volume administered.

Accidental overdose or suspected overdose without any association with laboratory abnormalities or clinical symptoms should not be considered as an AE. Overdose must be reported by the Investigator within 24 hours to Alexion regardless of whether an AE occurred.

The Sponsor does not recommend specific treatment for an overdose or suspected overdose.

In the event of an overdose or suspected overdose, the Investigator should:

- Contact the Medical Monitor immediately.
- Closely monitor the patient for any AE/SAE
- Obtain a plasma sample for PK analysis if requested by the Medical Monitor (determined on a case-by-case basis).
- For unblinded patients, document the quantity of the excess dose as well as the timing of the overdose in the CRF.

Decisions regarding dose interruptions will be made by the Investigator in consultation with the Medical Monitor based on the clinical evaluation of the patient.

## 8.6. Pharmacokinetics and Pharmacodynamics

- Blood samples for determination of serum drug concentrations and PD assessments will be collected before and after administration of study drug at the time points specified in the SoA (Section 1.3).
- Cerebrospinal fluid (CSF) samples for PK and PD assessments are optional at protocol-specified time points (Section 1.3). Samples will only be obtained from patients who consent to CSF collection (CSF Cohort). Collection should be performed at the screening visit after all other assessments are complete and eligibility has been confirmed.
  - Lumbar punctures will be performed to collect CSF samples and may only be performed on patients who have consented to CSF sample collection. Patients who are on therapeutic doses of anticoagulants will be deemed ineligible for the optional lumbar puncture procedures in this study. In addition, patients may be deemed ineligible to undergo lumbar puncture at the discretion of the Investigator after consideration of medical history, physical examination findings, laboratory assessments required as part of the SoA or other factors.
- Instructions for the collection and handling of biological samples will be provided by Alexion. The actual date and time (24-hour clock time) of each sample will be recorded on the eCRF and the central laboratory requisition form.
- Additional information on sample collection, including blood volume requirements, is provided in the Laboratory Manual.

- Baseline and trough PK and PD blood samples will be collected at predose, within 90 minutes before administering study drug at visits specified in the SoA (Section 1.3). The predose blood sample may be drawn through the venous access created for the dose infusion, prior to administration of the dose.
- Postdose PK and PD blood samples will be collected postdose, within 60 minutes after completing study drug infusion. The postdose blood samples will be drawn from the patient's opposite, noninfused arm.
- Blood samples at a nondosing visit can be collected at any time.
- In the event of an unscheduled visit, PK and PD blood sample will be collected as soon as possible.

## 8.7. Genetics

There are no prespecified genetic analyses in this study.

## 8.8. Biomarkers

### 8.8.1. Biomarker Research

Blood and urine samples for biomarker research will be collected from all patients, as described in Section 8.6, at the time points specified in the SoA (Section 1.3). Blood samples for biomarkers will be collected before administration of study drug, and biomarker urine samples may be collected at any time during the scheduled visit.

CSF samples are optional samples for biomarker research and should only be collected from patients who have consented to CSF sample collection. For biomarker CSF sample collection, refer to Section 8.6 and follow the same instructions on lumbar punctures for PK/PD assessments.

Biomarkers will be measured and include, but are not limited to, assessments of the following:

- Markers of neurodegeneration, such as neurofilament light chain (NfL)
- Complement proteins
- Markers of neuroinflammation, such as levels of proinflammatory cytokines and inflammatory cells

### 8.8.2. Future Biomarker Research

Blood samples for DNA and RNA isolation will be collected from patients who have consented to participate in the future genetic analysis component of the study. Future DNA and RNA testing on these samples includes, but is not limited to, specific candidate genes/genome-wide analysis.

Remaining samples from PK, PD, immunogenicity, and biomarker testing will be stored for future biomarker research. Analyses may be performed on biomarker variants thought to play a role in ALS activity/progression or treatment response to ravulizumab. These samples may also be used to develop methods, assays, prognostics and/or companion diagnostics related to the

study drug target, disease process, pathways associated with disease state, other complement-related diseases, and/or mechanism of action of the study drug.

Samples may be stored for a maximum duration according to local regulations following the last patient's last visit for the study at a facility selected by Alexion to enable further analyses.

## **8.9. Immunogenicity Assessments**

Antidrug antibodies (ADAs) to study drug will be evaluated in serum samples collected predose (within 5 to 90 minutes prior to the start of infusion of study drug) from all patients according to the SoA (Section 1.3).

Additionally, serum samples should also be collected at the final visit from patients who discontinued study drug or were withdrawn from the study.

Serum samples will be screened for antibodies binding to ravulizumab and the titer of confirmed positive samples will be reported. Other analyses may be performed to verify the stability of antibodies to ravulizumab and/or further characterize the immunogenicity of ravulizumab.

The detection and characterization of antibodies to ravulizumab will be performed using a validated assay method by or under the supervision of Alexion. Samples may be further characterized to determine the titer and the presence of neutralizing antibodies if deemed necessary. Samples may be stored for a maximum duration according to local regulations following the last patient's last visit for the study at a facility selected by Alexion to enable further analysis of immune responses to ravulizumab.

## **8.10. Medical Resource Utilization and Health Economics**

Medical resource utilization and health economics data associated with medical encounters will be collected in study eCRFs by the Investigator and study-site personnel for all patients throughout the study. Protocol-mandated procedures, tests, and encounters are excluded.

The data collected, which may be used to conduct exploratory economic analyses, include the following:

- Number of surgeries, and other selected procedures (inpatient and outpatient)
- Number and duration of hospitalizations
- Use of ventilator use and duration of use
- Use of wheelchair
- Use of feeding tube

## 9. STATISTICAL CONSIDERATIONS

Statistical methods described in this section will be further detailed in a separate Statistical Analysis Plan (SAP). The SAP will be developed and finalized prior to the database lock for the Randomized Controlled period. Statistical analyses will include tabulations of summary data, inferential analyses, by-patient listings and figures. Inference from efficacy analyses will be based on a 2-sided Type I error ( $\alpha$ ) = 5% unless stated otherwise. The summary statistics for continuous variables will include but not be limited to the number of patients, mean, standard deviation, minimum, median, and maximum. For categorical variables, frequencies and percentages will be presented. The baseline value for analysis and reporting will be based on the last nonmissing measurement on or prior to the first dose of study drug unless stated otherwise. The treatment groups for analysis and reporting will be based on the conventions outlined in Table 8. A 'Total' treatment group will be formed to report demographics, baseline characteristics, and other prestudy information including, medical and ALS history, and prior medications and SAEs captured between screening and first infusion. Details for imputation of efficacy data will be described in the SAP. Missing safety data will not be imputed.

Analyses will be performed using the SAS® software Version 9.4 or higher.

### 9.1. Statistical Hypotheses

#### 9.1.1. Primary Hypothesis

The primary null hypothesis is that the effect of ravulizumab is no different than placebo in functional decline measured by the change from baseline in ALSFRS-R total score at Week 50. The alternative hypothesis is that ravulizumab will slow the disease progression by reducing the decline from baseline in ALSFRS-R total score at Week 50 compared to placebo.

#### 9.1.2. Secondary Hypotheses

The null hypotheses associated with the secondary objectives are that ravulizumab is no different than placebo for the respective endpoints; the alternative hypotheses are described below:

1. **Time to VAFS:** The alternative hypothesis is that treatment with ravulizumab will prolong the time to VAFS compared to placebo.
2. **Change in SVC:** The alternative hypothesis is that treatment with ravulizumab will slow the decline from baseline in SVC at Week 50 compared to placebo.
3. **Change in muscle strength (HHD):** The alternative hypothesis is that treatment with ravulizumab will slow the decline from baseline in muscle strength at Week 50 compared to placebo.
4. **Neurofilament light chain (NfL) concentration:** The alternative hypothesis is that treatment with ravulizumab will lower the NfL concentration at Week 50 compared to placebo.

### 9.2. Sample Size Determination

The sample size calculations were based on information extracted from the PRO-ACT (Pooled Resource Open-Access ALS Clinical Trials, <https://nctu.partners.org/ProACT>) database

consisting of data pooled from 23 Phase 2/3 ALS clinical studies. Approximately 354 patients will be randomized to ravulizumab or placebo in a 2:1 ratio.

The mean change in ALSFRS-R total score in the placebo arm at Week 50 is estimated as -14.3 (assuming a monthly linear slope of decline of 1.19 calculated based on the proposed study inclusion criteria). Assuming a 30% relative reduction in monthly slope in the ravulizumab group, which is considered a clinically meaningful treatment effect (Castrillo-Viguera, 2010; Writing Group for Edaravone ALS Study, 2017), the mean change in ALSFRS-R total score at Week 50 is estimated as -10. A common standard deviation of 10.3 was estimated for the change from baseline in ALSFRS-R total score. A total of 282 patients will be required to ensure at least 90% nominal power based on a 2-sided t-test (Type I error = 0.05) for detecting a non-zero treatment effect for ALSFRS-R (defined as the difference between ravulizumab and placebo in the mean change from baseline in ALSFRS-R total score at Week 50). The total sample size is estimated as 354 after adjusting for a 20% dropout (Cudkowicz, 2013). Furthermore, assuming approximately 82% 1-year survival rate for placebo group and 50% relative reduction in hazard ratio for mortality due to treatment with ravulizumab, this sample size will provide at least 90% nominal power based on the primary analysis (CAFS).

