### 3. SAMPLE SIZE DETERMINATION

The sample size calculations were based on information extracted from the PRO-ACT (Pooled Resource Open-Access ALS Clinical Trials) database consisting of clinical trials data pooled from 23 Phase 2/3 ALS clinical trials. Approximately 354 patients will be randomized to ravulizumab or placebo in a 2:1 ratio.

The mean change in ALSFRS-R total score in the placebo arm at Week 50 is estimated as -14.3 (assuming a monthly linear slope of the decline of 1.19 calculated based on the proposed study inclusion criteria). Assuming a 30% relative reduction in the monthly slope in the ravulizumab group is considered a clinically meaningful treatment effect (Castrillo-Viguera, 2010; Writing Group for Edaravone ALS Study., 2017), the mean change in ALSFRS-R total score at Week 50 is estimated as -10. A common standard deviation (SD) of 10.3 was estimated for the change from Baseline in ALSFRS-R total score. A total of 282 patients will be required to ensure at least 90% nominal power based on a 2-sided t-test (Type I error = 0.05) for detecting a non-zero treatment effect for ALSFRS-R (defined as the difference between ravulizumab and placebo in the mean change from Baseline in ALSFRS-R total score at Week 50). The total sample size is estimated as 354 after adjusting for a 20% dropout (Cudkowicz, 2013). Furthermore, assuming approximately 82% 1-year survival rate for placebo group and 50% relative reduction in the HR for mortality due to treatment with ravulizumab, this sample size will provide at least 90% nominal power based on the primary analysis (CAFS).

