##### 5.3.3.1.2. Analytical Details for Sensitivity Analysis

The model will include the change from Baseline in ALSFRS-R total score at each study visit as the dependent variable and the following list of independent variables as fixed effects: actual time on the study (months), the interaction between time and treatment (0 = placebo, 1 = ravulizumab), age, sex, baseline ALSFRS-R total score, baseline SVC percent predicted,

months since first muscle weakness onset at Baseline, and the stratification factors. The participant-specific random slope will also be added to the model with an unstructured variance-covariance matrix to model the correlations among repeated measurements within each participant. The following covariance structures will be implemented if a convergence issue occurs in the specified order:

- Heterogeneous toeplitz (TOEPH)
- Heterogeneous autoregressive (1) (ARH (1))
- Heterogeneous compound symmetry (CSH)
- Toeplitz structure (TOEP)
- Autoregressive (1) (AR (1))
- Compound symmetry (CS)

The first covariance structure that converges will be used. The Kenward-Rogers method will be used to estimate the denominator degrees of freedom.

No imputation for the missing data will be performed after discontinuation (death or dropout) from the study, assuming the data are missing at random (MAR).

Section 6.2.9 provides details on implementing analysis windows.

A 2-sided p-value less than  $\alpha = 0.05$  associated with the higher mean change in ALSFRS-R total score in the ravulizumab group compared to placebo will indicate a statistically significant treatment benefit. The LS-means and the 95% CIs of the mean change from Baseline at Week 50 for each treatment arm and the difference between the arms will be calculated. The treatment effect will be evaluated via the estimated treatment-by-visit interaction term at Week 50 (Month 11.5). Details will be provided in a listing.

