##### **5.4.1.1.3. Other Analyses Related to VAFS and Components of VAFS (NIV, PAV and Mortality)**

An analysis for time (months) to NIV, PAV, and death will be performed separately with a Cox proportional hazards model similarly to that described in Section 5.4.1.1.2. However, these

analyses are different from the analyses of the VAFS components; for example, a participant may experience an event of NIV followed by death; hence, NIV will contribute to VAFS, but death will not. Hence the total number of participants experiencing any of these events may be greater than the total number of participants experiencing the VAFS event.

For VAFS and its components, the Kaplan-Meier curves by treatment group will be produced. Estimated survival probabilities at Week 50 (Month 11.5) will be provided for both treatment groups. The number and percentage of participants experiencing a VAFS event and its components will be provided. In addition, the number and percentage of deaths will be summarized by the associated reasons.

The number and percentage of participants with ventilator use (regardless of the number of hours) at least once during RCP, NIV, and PAV will be summarized. Details will be provided in listings.

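### The Week 50 planning changes of -14.3 and -10 are 12-month changes; at the SAP's Month 11.5 the difference is 4.1, not 4.3, and the sizing t-test reaches 90% power only if the Week 50 SD is 9.99 or less

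*Protocol*

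**What the plan says.** Protocol 9.2 gives the mean ALSFRS-R change "in the placebo arm at Week 50 is estimated as -14.3 (assuming a monthly linear slope of decline of 1.19" points per month). A 30% relative reduction in that slope gives -10 for ravulizumab, also labelled Week 50. On variability it says only: "A common standard deviation of 10.3 was estimated for the change from baseline in ALSFRS-R total score". SAP 3 repeats the paragraph, with the change "in the placebo arm at Week 50 is estimated as -14.3 (assuming a monthly linear slope of the decline of 1.19", and concludes: "A total of 282 patients will be required to ensure at least 90% nominal power based on a 2-sided t-test" at a Type I error of 0.05. Adjusting 282 for 20% dropout gives the planned 354, randomized 2:1.

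Elsewhere the SAP fixes what Week 50 means in months. SAP 5.3.3.1.2 evaluates the ALSFRS-R treatment effect through the "estimated treatment-by-visit interaction term at Week 50 (Month 11.5"). For the ventilation-free survival endpoint, SAP 5.4.1.1.3 says: "Estimated survival probabilities at Week 50 (Month 11.5) will be provided for both treatment groups". SAP 5.4.1.2.2 uses the same month for slow vital capacity.

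**The concern.** The sizing paragraph and the analysis sections assign different times to the same visit. A change built from a monthly slope depends directly on the number of months, so calling a 12-month change a Week 50 change overstates the planned treatment difference at that visit. The 282 and the 354 both rest on that difference, and the stated power is only just above its 90% threshold. Because the SD is undated, a reader cannot tell whether it shares the same 12-month basis, and so cannot tell whether the power statement is true for Week 50.

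**Working it through.** **Inputs.** From Protocol 9.2 and SAP 3: placebo slope 1.19 points per month; 30% relative reduction, so 1.19 x 0.7 = 0.833 on ravulizumab; SD 10.3; two-sided alpha 0.05; 2:1 allocation, so 282 splits as 188:94.

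**1. Reproduce the plan's figures.** Power is from the noncentral t distribution with 280 degrees of freedom and noncentrality difference / (SD x sqrt(1/188 + 1/94)), where the square root is 0.1263. With difference 14.3 - 10 = 4.3 and SD 10.3, noncentrality is 4.3 / 1.301 = 3.305 and power is 90.9%. The smallest 2:1 total reaching 90% is 276, so 282 is consistent with the stated inputs. Then 282 / 0.8 = 352.5, which becomes 354 for an exact 2:1 split. The method is not in question.

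**2. Find the time behind the means.** 1.19 x 12 = 14.28 and 0.833 x 12 = 9.996, matching -14.3 and -10. Rounding does not rescue 11.5 months. If the slope lies between 1.185 and 1.195 and the mean between 14.25 and 14.35, the implied time runs from 14.25 / 1.195 = 11.92 to 14.35 / 1.185 = 12.11 months.

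**3. Convert Week 50 to months.** The SAP states Month 11.5. Its month formula in Table 17 (12 x days / 365.25), applied to 350 days, gives 11.50. The protocol's equating of Week 26 with 6 months (sections 1.2 and 3.1) gives 6 x 50 / 26 = 11.54.

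**4. Recompute the means.** 1.19 x 11.5 = 13.685 and 0.833 x 11.5 = 9.580, a difference of 4.1055. The 12-month difference is 4.284, and 4.284 / 4.1055 = 1.043, so the stated effect is 4.3% too large for the named visit.

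**5. Recompute power at 188:94.** The last two rows assume that 10.3 is a 12-month SD and apply a shrinkage rule to it. Both rules are assumptions; the documents give none.

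| Case | Difference | SD | Power | Evaluable N for 90% |
|---|---|---|---|---|
| As stated | 4.3 | 10.3 | 90.9% | 276 |
| Month 11.5, 10.3 is the Week 50 SD | 4.1055 | 10.3 | 88.2% | 300 |
| Month 11.5, SD shrinks with square root of time: 10.3 x sqrt(11.5/12) | 4.1055 | 10.08 | 89.5% | 288 |
| Month 11.5, SD shrinks in proportion to time: 10.3 x 11.5/12 | 4.1055 | 9.87 | 90.7% | 276 |

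**6. Break-even at 282.** With difference 4.1055, power is 90% at SD 9.99 (10.03 by the normal approximation). With SD 10.3, it is 90% at difference 4.23. The slopes differ by 0.357 points a month, so that is 4.232 / 0.357 = 11.85 months of decline.

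**The case against.** The strongest reply is that no power shortfall has been shown. The SD comes from pooled trial data not reproduced in the documents, and the power range of 88.2% to 90.7% straddles the threshold. If 10.3 was taken at 12 months, like the means beside it, and scales with time, the standardised effect does not change: 4.284 / 10.3 and 4.1055 / 9.87 are both 0.416. The plan's own ALSFRS-R model has a patient-specific random slope, which leans that way. With a random slope plus residual, 90% holds at Month 11.5 if slope variation supplies at least about 72% of the 12-month variance. (The variance must fall from 10.3² = 106.1 to 9.99² = 99.8; slope variance is then at least 6.25 / (12² - 11.5²) = 0.532, and 144 x 0.532 / 106.1 = 0.72.) This stands as a reason to keep the power conclusion conditional. It does not correct the means, and it depends on the SD time point that the plan omits.

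Second, the primary analysis is an adjusted rank analysis (CAFS) in which, under SAP 5.3.1, survivors are compared on monthly slope; the planned slopes are the same whether follow-up is called 11.5 or 12 months. That also stands, and the CAFS power sentence is not tested here. But 282 and 354 are derived from the t-test, with CAFS power added afterwards.

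Third, 4.3 and 10.3 are the figures actually used to choose the sample size, and 12 months may have been intended, since the same paragraph quotes a 1-year survival rate. Yet the text names Week 50 for both means and for the treatment effect.

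Finally, the study met its futility criterion, all p-values are descriptive (SAP 5.1), and the note to file says Amendment 6 was never implemented. These facts limit the practical weight. They do not make the Week 50 figures right, and SAP version 2, written after futility, still carries the paragraph.

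**Conclusion.** The concern holds. The Week 50 labels on -14.3 and -10 are wrong by the documents' own slopes and month convention: the values should be -13.7 and -9.6, a difference of 4.1. That part needs no outside assumption.

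The effect on power is conditional and small. At most it is a fall from 90.9% to 88.2%, if 10.3 is the Week 50 SD, which is 1.8 points below the stated minimum. That is the plainest reading, because the SD sentence sits between Week 50 means and a Week 50 treatment effect and names no other visit. If 10.3 is a 12-month SD, the claim may just fail or just hold. The statement of at least 90% power therefore rests on a Week 50 SD of 9.99 or less, which neither document states. The conclusion covers the unadjusted sizing t-test only.

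**What to change.** In Protocol 9.2 and SAP 3:

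- Restate the Week 50 means as -13.7 and -9.6, difference 4.1, and note that 282 was obtained from the 12-month difference so that its origin stays traceable.
- State the time point of the SD of 10.3.
- Restate the t-test power to match: about 88% if 10.3 is the Week 50 SD; otherwise give the Week 50 SD used and the power it yields.
- Leave the CAFS power sentence as a separate statement.

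The sample size should not be raised. The cost is a wording change in two places; no analysis or result changes.
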